6.2 Epirubicin (Ellence)

Availability: Epirubicin is commercially available.

Product description: Epirubicin is available in polypropylene single-use vials containing 2 mg epirubicin hydrochloride per mL as a sterile, preservative-free ready-to-use solution in 50 mg and 200 mg vials.

Solution preparation: Epirubicin is available as a preservative-free, ready-to-use solution.

Storage requirements: Store refrigerated between 2°C and 8°C (36°F and 46°F). Do not freeze. Protect from light.

Stability: Epirubicin should be used within 24 hours of first penetration of the rubber stopper.

Route of administration: Intravenous administration of epirubicin should be performed with caution. It is recommended that epirubicin be administered into the tubing of a freely flowing intravenous infusion (0.9% sodium chloride or 5% glucose solution) over a period of 3 to 5 minutes. This technique is intended to minimize the risk of thrombosis or perivenous extravasation, which could lead to severe cellulites, vesication, or tissue necrosis. A direct push injection is not recommended due to the risk of extravasation, which may occur even in the presence of adequate blood return upon needle aspiration. Venous sclerosis may result from injection into small vessels or repeated injections into the same vein.

Pregnancy: Women should avoid becoming pregnant while on therapy. Breastfeeding should be discontinued during therapy.

Expected adverse events:

Hematologic: A dose-dependent, reversible leukopenia and/or neutropenia is the predominant manifestation of hematologic toxicity. Severe thrombocytopenia and anemia may also occur.

Gastrointestinal: Nausea and vomiting, diarrhea, stomatitis

Dermatologic: Alopecia, flushes, skin and nail hyperpigmentation, photosensitivity, hypersensitivity to irradiated skin.

Extravasation: Infiltration can cause severe inflammation, tissue necrosis, and ulceration. If the drug is infiltrated, consult institutional policy, apply ice to area, and elevate the limb. May require debridement.

Cardiac: Anthracycline-induced cardiac toxicity may be manifested by early or late events. Early cardiac toxicity consists mainly of sinus tachycardia and/or ECG abnormalities such as non-specific ST-T wave changes, but tachyarrhythmias, bradycardia, as well as atrioventricular and bundle-branch block have also been reported. Delayed cardiotoxicity results from a characteristic cardiomyopathy that is manifested by reduced LVEF and/or signs and symptoms of congestive heart failure.

The probability of developing CHF increases with increasing cumulative doses of epirubicin. The risk of developing CHF in the absence of other cardiac risk factors increases steeply after an epirubicin cumulative dose of 900 mg/m².

Secondary Leukemia: The occurrence of secondary acute myelogenous leukemia has been reported in patients treated with anthracyclines.

Miscellaneous: Allergic reaction, anaphylaxis.

6.3 Ifosfamide (Ifex)

Availability: Ifosfamide is commercially available.

Product description: Ifosfamide is available as a powder for reconstitution in 1 and 3 g vials.

Solution preparation: Dilute powder with SWI or NS to a concentration of 50 mg/mL as follows. **DO NOT USE BACTERIOSTATIC SWI OR NS** - incompatible; solution is stable for 7 days at room temperature and 6 weeks under refrigeration

1 g vial = 20 mL

3 g vial = 60 mL

Storage and Stability: Further dilution in NS, D5W or LR is stable for 7 days at room temperature and 6 weeks under refrigeration. Compatible with mesna in NS for up to 9 days at room temperature. Store intact vials at room temperature or under refrigeration.

Route of administration: Administer ifosfamide IVPB over 90 minutes. Adequate hydration (at least 2 L/day) of the patient during therapy is recommended to minimize the risk of hemorrhagic cystitis. Mesna should be administered concomitantly, 4 hours after and 8 hours after ifosfamide administration.

Pregnancy: Women should avoid becoming pregnant while on therapy. Breastfeeding should be discontinued during therapy.

Expected adverse events:

Central nervous system: Somnolence, confusion, hallucinations in 12% and coma (rare) have occurred and are usually reversible; usually occur with higher doses or in patients with reduced renal function; depressive psychoses, polyneuropathy. **Note:** CNS depression can be reversed with methylene blue (50 mg intravenously) and methylene blue is recommended for prophylaxis for subsequent doses if the patient has CNS manifestations with the first dose.

Dermatologic: Alopecia occurs in 50% to 83% of patients 2-4 weeks after initiation of therapy; may be as high as 100% in combination therapy. Phlebitis, dermatitis, nail ridging, skin hyperpigmentation, impaired wound healing.

Gastrointestinal: Nausea and vomiting in 58% of patients is dose and schedule related (more common with higher doses and after bolus regimens); nausea and vomiting can persist up to 3 days after therapy; also anorexia, diarrhea, constipation, transient increase in LFTs and stomatitis noted.

Genitourinary: Hemorrhagic cystitis has been frequently associated with the use of ifosfamide; a urinalysis prior to each dose should be obtained; **ifosfamide should never be administered without a uroprotective agent (MESNA)**; hematuria has been reported in 6% to 92% of patients; renal toxicity occurs in 6% of patients and is

manifested as an increase in BUN or serum creatinine and is most likely related to tubular damage; renal toxicity, including ARF, may occur more frequently with high-dose ifosfamide; metabolic acidosis may occur in up to 31% of patients.

Endocrine & metabolic: SIADH

Hematologic: Myelosuppression: Leukopenia is mild to moderate, thrombocytopenia and anemia are rare. However, myelosuppression can be severe when used with other chemotherapeutic agents or with high-dose therapy; be cautious with patients with compromised bone marrow reserve

Respiratory: Nasal stuffiness, pulmonary fibrosis

Cardiovascular: Cardiotoxicity

Miscellaneous: Immunosuppression, sterility, possible secondary malignancy, allergic reactions

6.4 Mesna (*Mesnex*)

Availability: Mesna is commercially available.

Product description: Mesna is available as a sterile, preservative-free aqueous 100 mg/mL solution in 200 mg ampules or 1 g multidose vials. Mesna tablets are available as a white, oblong, scored, film coated 400 mg tablet.

Mechanism of action: Mesna is a uroprotectant whose oxidized form dimesna binds to and inactivates acrolein, a urotoxic metabolite of cyclophosphamide and ifosfamide.

Solution preparation: Mesna can be diluted in D5W or NS to a final concentration of 1-20 mg/mL.

Storage and Stability: Diluted solutions are chemically and physically stable for 24 hours at room temperature; polypropylene syringes are stable for 9 days at refrigeration or room temperature; injection diluted for oral administration is stable 24 hours at refrigeration

Route of administration: Mesna may be mixed in same bag as ifosfamide or administered separately IVPB over 15 minutes.

Mesna injection may also be administered orally. For oral administration, injection may be diluted in 1:1, 1:2, 1:10, 1:100 concentrations in carbonated beverages (cola, ginger ale, Pepsi®, Sprite®, [name]®, etc), juices (apple or orange), or whole milk (chocolate or white), and is stable 24 hours at refrigeration. Mesna tablets should be given orally and absorption is not affected by food. Mesna tablets are approximately 50% bioavailable and are generally dosed at 2 & 6 hours after the first mesna dose, which is usually given intravenously, to account for the delayed absorption with an oral vs. the intravenous product

Pregnancy: Women should avoid becoming pregnant while on therapy. Breastfeeding should be discontinued during therapy.

Expected adverse events:

Cardiovascular: Hypotension

Central nervous system: Malaise, headache

Gastrointestinal: Diarrhea, nausea, vomiting, bad taste in mouth, soft stools

Neuromuscular & skeletal: Limb pain

Dermatologic: Skin rash, itching

6.5 Pegfilgrastim (Neulasta)

Availability: Pegfilgrastim is commercially available.

Product Description: Neulasta™ is supplied as a preservative-free solution containing 6 mg (0.6 mL) of pegfilgrastim (10 mg/mL) in a single-dose syringe with a 27 gauge, 1/2 inch needle with an UltraSafe® Needle Guard. Neulasta™ is provided in a dispensing pack containing one syringe (NDC 55513-190-01).

Storage and Stability: Neulasta™ should be stored refrigerated at 2° to 8°C (36° to 46°F); syringes should be kept in their carton to protect from light until time of use. Shaking should be avoided. Before injection, Neulasta™ may be allowed to reach room temperature for a maximum of 48 hours but should be protected from light. Neulasta™ left at room temperature for more than 48 hours should be discarded. Freezing should be avoided; however, if accidentally frozen, Neulasta™ should be allowed to thaw in the refrigerator before administration. If frozen a second time, Neulasta™ should be discarded.

Route of Administration: The recommended dosage of Neulasta™ is a single subcutaneous (SC) injection of 6 mg administered once per chemotherapy cycle. Neulasta™ should not be administered in the period between 14 days before and 24 hours after administration of cytotoxic chemotherapy. The 6 mg fixed-dose formulation should not be used in infants, children, and smaller adolescents weighing less than 45 kg. Neulasta™ should be visually inspected for discoloration and particulate matter before administration. Neulasta™ should not be administered if discoloration or particulates are observed.

Neulasta™ is supplied in prefilled syringes with UltraSafe® Needle Guards. Following administration of Neulasta™ from the prefilled syringe, the UltraSafe® Needle Guard should be activated to prevent accidental needle sticks. To activate the UltraSafe® Needle Guard, place your hands behind the needle, grasp the guard with one hand, and slide the guard forward until the needle is completely covered and the guard clicks into place. NOTE: If an audible click is not heard, the needle guard may not be completely activated. The prefilled syringe should be disposed of by placing the entire prefilled syringe with guard activated into an approved puncture-proof container.

Pregnancy: Women should avoid becoming pregnant while on therapy. Breastfeeding should be discontinued during therapy.

Expected Adverse Events:

Bone pain was the most frequent adverse event attributable to pegfilgrastim in clinical trials. Hypoxia was observed in one patient. Toxicities associated with the parent compound, filgrastim include:

Central nervous system: Neutropenic fever, fever.

Dermatologic: Alopecia.

Gastrointestinal: Nausea, vomiting, diarrhea, mucositis, splenomegaly (this occurs more commonly in patients with cyclic neutropenia/congenital agranulocytosis who received S.C. injections for a prolonged (>14 days) period of time; ~33% of these

patients experience subclinical splenomegaly; ~3% of these patients experience clinical splenomegaly).

Neuromuscular & skeletal: Medullary bone pain (24% incidence--this occurs most commonly in lower back pain, posterior iliac crest, and sternum and is controlled with non-narcotic analgesics), weakness.

Cardiovascular: Chest pain, fluid retention, transient supraventricular arrhythmia, pericarditis.

Central nervous system: Headache.

Dermatologic: Skin rash.

Gastrointestinal: Anorexia, stomatitis, constipation.

Hematologic: Leukocytosis.

Local: Pain at injection site, thrombophlebitis.

Respiratory: Dyspnea, cough, sore throat.

Miscellaneous: Anaphylactic reaction.

7. CORRELATIVE / SPECIAL STUDIES

7.1 Angiogenic Biomarkers

Plasma will be collected for measurement of tumorigenic and angiogenic markers including p-ERK, VEGF, sVEGFR2, and bFGF at baseline, week 2 (after sorafenib run-in), and then every 3 weeks through completion of treatment. Blood samples (10 mL) will be drawn using venipuncture into a Vacutainer containing potassium EDTA and inverted gently several times to mix with anticoagulant. Within 10-15 minutes after collecting, blood samples will be centrifuged in a refrigerated (4°C) centrifuge for 10 minutes to separate the plasma. If a refrigerated centrifuge is not available, the tubes should be chilled in an ice bath for 5-15 minutes and then placed in a standard centrifuge for 10 minutes to separate the plasma. The plasma will be transferred to polypropylene tubes and frozen at -70°C or lower. The tubes will be labeled with the investigator's name, study number, and subject's study number, and time and date of the sample acquisition.

Fresh tumor tissue will be collected when possible at baseline and at time of resection. Tissue will be immediately frozen with liquid nitrogen and stored at -70°C or lower. Tumor tissue will be mechanically homogenated for 5 minutes on ice in 1 ml of extraction buffer per 100 mg tissue wet weight, and extract obtained after centrifugation for 20 minutes at 4°C will be transferred to polypropylene tubes and frozen at -70°C or lower. The tubes will be labeled with the investigator's name, study number, and subject's study number, and time and date of the sample acquisition.

Quantitative enzyme-linked immunosorbent assays (ELISA) for p-ERK, VEGF, sVEGFR2, and bFGF will be performed on plasma and tumor extracts using commercial kits. Manufacturers' protocols will be followed and samples are to be measured in duplicate.

Paraffin block of the primary tumor biopsy and resected tumor will be obtained. Representative areas from each whole-mount paraffin block chosen as the best composite representation of tumor based on H&E morphology will be placed in

standard-sized tissue cassettes. These will be re-embedded, sectioned at 4 μm , and mounted on poly-L-lysine-coated slides for immunohistochemistry. Sections of paraffin embedded tissue will be deparaffinized and rehydrated. After appropriate antigen retrieval methods, staining with commercial antibodies for p-ERK, VEGF-R2, phospho-VEGF-R2, PDGFR, and phospho-PDGFR will be performed using an automated Dako immunostainer. Staining will be visualized by incubating the slides with 3,3'-diaminobenzidine solution, after which they will be rinsed, counterstained with hematoxylin, dehydrated in a Leica Autostainer XL, coverslipped, and reviewed by a single experienced pathologist who will score the percentage of positively staining cells

8. STUDY PROCEDURES AND SCHEDULE OF EVENTS

8.1 Subject Registration

Written informed consent must be obtained before any study specific medical procedures are performed.

All patients must be registered with the Oregon Health & Science University Cancer Center.

8.2 Baseline Screening

To be completed within 6 weeks of registration:

CT of Chest

CT or MRI of primary disease site

To be completed within 4 week of registration:

History & Physical, including vitals, PS

EKG

MUGA or ECHO

To be completed within 1 week of registration:

Labs, pregnancy test, urinalysis

(Pregnancy test must be repeated prior to dispensing Sorafenib to the patient if completed >7 days before treatment start)

8.3 Study Visits

See table 8.7

Toxicities and adverse experiences will be assessed at each visit using the NCI Common Toxicity Criteria for Adverse Events v4.0 (<http://ctep.cancer.gov>).

Assessment of study drug attribution will be made by an Investigator. **Acute and long-term radiation toxicity will be assessed for the following CTCAE categories: 1) Injury, poisoning and procedural complications: Dermatitis radiation 2) Musculoskeletal and connective tissue disorders: Fibrosis (superficial and/or deep) 3) other appropriate Musculoskeletal and connective tissue disorders AEs appropriate to limb function.**

8.4 Pathology Sample Submission

All pathology slides from the initial diagnostic biopsy and the post-chemoradiation

excision must be submitted for central review at OHSU by a pathologist experienced in sarcoma. For the post therapy excision, the specimen should be sectioned parallel to the long axis of the tumor; a full face of the plane of greatest cross sectional area should be fixed and blocked in, up to 20 sections. If there are central cystic necrotic areas, they can be noted in a specimen diagram and not sampled.

8.5 Assessment of Wound Complications

An accurate assessment of post-operative wound complications is vital for the accurate reporting of toxicity associated with this regimen. Major wound complications will be defined as described by O'Sullivan et. al. in the prospective, randomized study of preoperative vs. postoperative radiation.⁷

A major wound complication is defined as a secondary operation under general or regional anesthesia for wound repair (debridement, operative drainage, and secondary wound closure including rotationplasty, free flaps, or skin grafts), or wound management without secondary operation. Wound management includes an invasive procedure without general or regional anesthesia (such as aspiration of seroma), readmission for wound care such as intravenous antibiotics, or persistent deep packing for 120 days or longer.

8.6 Follow-up

Follow-up for all patients registered on this study, including those who do not receive any protocol therapy, will be required until the patient's death. Follow-up after completion of protocol therapy will be limited to monitoring for 1) development of local tumor recurrence, 2) development of distant metastatic disease, 3) survival, and 4) late toxicity, including limb function impairment and secondary malignancy. Follow-up reports are due every 4 months.

8.7 Schedule of Events

	Prior to Registration	Prior to Day 1 of each cycle*	Time of Pre-Surgical Restaging**	Post Treatment Follow-up
Tests & Observations				
History and Progress Notes	X	X	X	X
Physical Examination	X	X	X	X
Pulse, Blood Pressure###	X	X	X	X
Height/Weight***	X	X		
Performance Status	X	X	X	X
Treatment Toxicity Assessment		F	F	F
Pathology Review	A		A	
Laboratory Studies				
CBC, Differential, Platelets	X	B,C	X	PRN
Serum Chemistries#	X	B,C	X	PRN
Urinalysis	X	C		
Pregnancy Test##	X	X		
INR	X	H		
EKG	X			PRN
MUGA or ECHO	X		X	D
Blood for correlative studies (Section 7.1)	X	X	X	
Staging				
Chest CT	X		X	E
MRI or CT of primary site	G		G	E

* To be performed within 1 week of each chemotherapy cycle

** After completion of cycle 3 of chemoradiotherapy and within 4 weeks of surgery

*** Height only needs to be checked prior to cycle #1 if the patient's height is stable (i.e. not currently in puberty).

Electrolytes (including Phos, Mg), BUN, creatinine, bilirubin, AST, ALT, alkaline phosphatase

For women of childbearing potential. Screening pregnancy test does not need to be repeated if within 7 days of start of Sorafenib run-in. Will be repeated prior to each cycle of chemotherapy.

Blood pressure to be monitored weekly during the first 6 weeks of protocol treatment

A Initial diagnostic pathology specimen as well as post-operative specimen must be submitted for central review. Both specimens may be submitted together after surgery

B To be checked once weekly during each cycle or as clinically indicated

C Must be checked within 24 hours prior to each chemotherapy cycle

D As clinically indicated

E Post-treatment imaging studies for disease recurrence is at investigator's discretion. It is suggested that a chest CT or chest X-ray be performed every 4 months for the first 2 years, every 6 months for the 3rd year, and yearly for the 4th and 5th year. It is suggested that MRI or CT of the primary site be obtained yearly for the first 3 years.

F Toxicity assessments per CTCAE v 4.0 (See section 8.3). Long term follow-up for radiation toxicity and limb function required per section 8.3

G An MRI or CT of the primary tumor should be performed within 6 weeks prior to registration and again prior to surgery per standard care decision of the subject's surgeon

H INR should be closely monitored for patients receiving warfarin. INR does not need to be monitored during study for patients not receiving warfarin.

9. MEASUREMENT OF EFFECT

9.1 Pathologic Response

All specimens of primary tumor will be examined for pathologic response at the time of surgery. The study pathologist will estimate the amount of viable tumor, and report the percentage of necrosis. For purpose of analysis, tumors will be classified as either $\geq 95\%$ necrosis or $< 95\%$ necrosis.

9.2 Radiographic and Clinical Response

The radiographic and/or clinical response of the primary tumor to preoperative therapy will be evaluated. For subjects with stage IIb or III disease, the primary lesion will serve as the sole target lesion and will be recorded and measured at baseline. For patients with stage IV disease, target lesions will be chosen according to RECIST procedure. The longest diameter (LD) of the target lesions will be measured and reported as the baseline LD. The baseline LD will be used as reference to further characterize the objective tumor response of the measurable dimension of the disease.

Response and progression will be evaluated in this study using the new international criteria proposed by the Response Evaluation Criteria in Solid Tumors (RECIST) Committee.⁵⁶ Changes in only the largest diameter (unidimensional measurement) of the tumor lesions are used in the RECIST criteria.

9.3 Response Criteria

9.3.1 Evaluation of target lesions

Complete Response (CR):	Disappearance of all target lesions
Partial Response (PR):	At least a 30% decrease in the sum of the longest diameter (LD) of target lesions, taking as reference the baseline sum LD
Progressive Disease (PD):	At least a 20% increase in the sum of the LD of target lesions, taking as reference the smallest sum LD recorded since the treatment started or the appearance of one or more new lesions
Stable Disease (SD):	Neither sufficient shrinkage to qualify for PR nor sufficient increase to qualify for PD, taking as reference the smallest sum LD since the treatment started

9.3.2 Evaluation of best overall response

The best overall response is the best response achieved prior to surgical resection of the target lesion.

Target Lesions	New Lesions	Overall Response
CR	No	CR
PR	No	PR
SD	No	SD
PD	Yes or No	PD
Any	Yes	PD

Note:

In some circumstances, it may be difficult to distinguish residual disease from normal tissue. When the evaluation of complete response depends upon this determination, this will be determined at the time of surgical resection.

9.4 Confirmatory Measurement/Duration of Response

9.4.1 Confirmation

Given that the target lesion will be surgically removed after the first evaluation for response, no confirmatory scans will be able to be performed.

9.4.2 Duration of overall response

The duration of overall response is measured from the time measurement criteria are met for CR or PR (whichever is first recorded) until the first date that recurrent or progressive disease is objectively documented (taking as reference for progressive disease the smallest measurements recorded since the treatment started).

The duration of overall CR is measured from the time measurement criteria are first met for CR until the first date that recurrent disease is objectively documented.

9.4.3 Duration of Stable Disease

Stable disease is measured from the start of the treatment until the criteria for progression are met, taking as reference the smallest measurements recorded since the treatment started.

9.5 Time-to-Event Measures

9.5.1 Time to Local Recurrence

Defined as the duration of time from surgical resection of the primary tumor until local recurrence (amputated patients excluded).

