1. OBJECTIVES

- **Primary objective**
 - To determine the pathologic response rate ($\geq 95\%$ necrosis) after preoperative treatment with sorafenib, epirubicin, ifosfamide, and hypofractionated radiation for high risk soft tissue sarcomas of the extremities or body wall.
- **Secondary objectives**
 - To further characterize the safety of sorafenib plus chemoradiotherapy, including wound complication rate
 - To estimate time-to-event rates, including overall survival, overall disease-free survival, distant disease-free survival, and local disease-free survival in patients with high risk soft tissue sarcomas of the extremities or body wall treated with preoperative sorafenib plus chemoradiotherapy and postoperative sorafenib plus chemotherapy.

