2. BACKGROUND

2.1 Soft-Tissue Sarcomas

Soft-tissue sarcomas are a group of heterogeneous, rare tumors that are diagnosed in approximately 8,000 patients per year in the United States. While limb-salvage procedures combining wide excision with radiation therapy achieve local control in up to 90% of patients with extremity soft-tissue sarcomas, approximately half of patients with high-grade, >5 cm, deep tumors will die from metastatic disease.¹⁻⁴ The outcome of these patients is unacceptable. Improving the survival of patients diagnosed with such high-risk tumors is a priority.

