3. PATIENT SELECTION

3.1 Eligibility Criteria

- 3.1.1 Histologically confirmed, soft-tissue sarcoma:** excluding rhabdomyosarcoma (pleomorphic rhabdomyosarcoma patients are eligible), Ewing's, PNET, osteosarcoma, or gastrointestinal stromal tumor
- 3.1.2 AJCC (7th Edition) Stage IIb, III, or IV patients planned for resection of the primary tumor**
- >5 cm in greatest dimension
 - Intermediate or High-Grade (see 3.1.4)
 - Superficial or Deep
- 3.1.3 Sarcoma located on upper (includes shoulder) or lower (includes hip) extremities or on body wall**
- 3.1.4 Intermediate or High-Grade:** Grades 2 or 3 on scale of 1-3
- 3.1.5 LVEF $\geq 50\%$**
- 3.1.6 Required initial laboratory values:**
- | | |
|------------|--------------------------|
| ANC | ≥ 1500 / μ L |
| Hgb | ≥ 9.0 g/dL |
| Platelets | $\geq 100,000$ / μ L |
| Creatinine | ≤ 1.5 x ULN |
| Bilirubin | ≤ 1.5 mg/dL |
| AST/ALT | ≤ 1.5 x ULN |
- 3.1.7 INR < 1.5 or a PT/PTT within normal limits.** Patients receiving anti-coagulation treatment with an agent such as warfarin or heparin **may** be allowed to participate. For patients on warfarin, the INR should be measured prior to initiation of sorafenib and monitored at least weekly, or as defined by the local standard of care, until INR is stable.
- 3.1.8 No prior chemotherapy, radiation, or biotherapy**
- 3.1.9 No major surgery within 4 weeks prior to study entry**
- 3.1.10 No contraindications to limb-sparing surgery.** Patient should be evaluated by a surgeon who specializes in sarcoma resections prior to study enrollment to ensure pt is a candidate for limb-sparing surgery.
- 3.1.11 No severe peripheral vascular disease**
- 3.1.12 Adequate contraception must be used and patients must not be pregnant or breastfeeding.** Women of childbearing potential and men must

agree to use adequate contraception (barrier method of birth control) prior to study entry and for the duration of study participation. Men and women should use adequate birth control for at least thirty days after the last administration of sorafenib.

3.1.13 Women of childbearing potential must have negative serum pregnancy test performed within 7-days prior to registration.

3.1.14 Age \geq 18

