Resectability will depend upon the judgment of the operating surgeon. For the extremities, resection must be limb salvage procedure. For other anatomic areas, it must be the judgment of the operating surgeon that he/she may reasonably expect to obtain negative margins. Extremity patients who are not resectable without amputation may be amputated, and should complete chemotherapy per protocol. Unresectable tumors elsewhere may be palliated with additional chemotherapy, per protocol. Patients who would benefit from additional radiation therapy will be withdrawn from protocol therapy.

Note that documentation of wound complications is an integral part of this clinical trial. Wound complications are defined in section 8.5 and must be accurately recorded and reported to the coordinating center.

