9.5.2 Local Disease-Free Survival

Defined as the duration of time from surgical resection of the primary tumor until local recurrence or death, whichever occurs first.

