11.1.2 Secondary endpoint

Secondary endpoints include level of toxicity, wound complication rate, overall survival, overall disease-free survival, distant disease-free survival and local disease-free survival.

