11.2 Statistical analysis plan

Descriptive statistical analysis will be conducted for the primary and secondary endpoints. The proportion with 95% confidence interval will be summarized for the categorical variables. Method of Kaplan-Meier will be used to estimate the survival functions.

We will also conduct exploratory analysis to investigate levels of tumor proliferation and angiogenic markers including p-ERK, VEGF, sVEGFR-2, bFGF in the plasma and tumor tissue at baseline, during, and after treatment with sorafenib plus chemoradiotherapy and to evaluate expression of tumorigenic and angiogenic factors including p-ERK, VEGF-R2 and PDGFR in tumor tissue by immunohistochemical staining. These analyses will be conducted in an exploratory manner with the aim of generating clinically and biologically interesting hypotheses.

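### Time to local recurrence has no stated rule for death; under the plan's only method, Kaplan-Meier, the recurrence proportion would be modestly overstated

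*Combined protocol and SAP*

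**What the plan says.** Section 9.5 gives two local measures. Time to local recurrence (9.5.1) reads "Defined as the duration of time from surgical resection of the primary tumor until local recurrence (amputated patients excluded". Local disease-free survival (9.5.2) reads "Defined as the duration of time from surgical resection of the primary tumor until local recurrence or death, whichever occurs first". Both start the clock at resection. Only the second counts death as an event, and only the first removes amputated patients.

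On method, section 11.2 has one sentence for time-to-event data: "Method of Kaplan-Meier will be used to estimate the survival functions". No competing-risk estimator is mentioned, and nothing says how a death without local recurrence enters 9.5.1.

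On status, section 11.1.2 states: "Secondary endpoints include level of toxicity, wound complication rate, overall survival, overall disease-free survival, distant disease-free survival and local disease-free survival". The secondary objective in section 1 begins "To estimate time-to-event rates, including overall survival" and goes on to name the same four survival endpoints. Time to local recurrence is in neither list, although both lists are worded as open ones.

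On amputation, section 3.1 requires "No contraindications to limb-sparing surgery" at entry, while section 4.4 provides that "Extremity patients who are not resectable without amputation may be amputated, and should complete chemotherapy per protocol".

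**The concern.** When the event is recurrence alone, a patient who dies without recurring can no longer have the event. Kaplan-Meier treats such a patient as censored, that is, as still able to recur at the same rate as those under observation. One minus Kaplan-Meier then describes recurrence in a setting where nobody dies, and it is never below the proportion of patients who actually recur. The gap widens as more patients die first.

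Deaths are not rare here. The background (2.1) says that about one in two patients with large, deep, high-grade tumours dies of metastases. Stage IV patients are eligible (3.1.2) and, unlike in 9.5.3 and 9.5.4, are not set aside in 9.5.1. Follow-up runs to death (8.6). A reader would probably take the result as a local control rate and compare it with the background statement that limb salvage with radiation can "achieve local control in up to 90% of patients with extremity soft-tissue sarcomas".

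The amputation exclusion raises a separate question. Patients enter as limb-salvage candidates, so an amputation on study reflects something found or decided after enrolment, plausibly linked to the local tumour. Removing these patients changes the population being described.

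**Working it through.** **The plan's own figures.** The documents give no figure for local recurrence. The only design calculation (11.3: 20 patients, 25% against 52%, one-sided 5%) reproduces. Success at 9 or more of 20 has exact type I error 0.041 and power 0.802. It does not involve this measure.

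**Inputs for the competing-risk check.**
- L, the true cumulative proportion with local recurrence: 10%, an assumption suggested by the local control figure of up to 90% in 2.1.
- D, the proportion dying first without local recurrence, at the same time point: 16%, 30% or 50%, also assumptions. The 16% is 100% − 84%, from the 2-year survival in the earlier regimen (2.4). The interval there, 66% to 100%, allows 0% to 34% dead. The 50% comes from the statement in 2.1 on metastatic death, which has no time horizon. Both sources count all such deaths, including any after a local recurrence.

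**Formula, constant cause-specific hazards.** Total cumulative hazard H = −ln(1 − L − D). Local share h = H × L/(L + D). One minus Kaplan-Meier with deaths censored = 1 − exp(−h). Aalen-Johansen cumulative incidence targets L itself.

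| L | D | H | h | 1 − KM | Excess (points) |
|---|---|---|---|---|---|
| 10% | 16% | −ln(0.74) = 0.301 | × 10/26 = 0.116 | 10.9% | 0.9 |
| 10% | 30% | −ln(0.60) = 0.511 | × 10/40 = 0.128 | 12.0% | 2.0 |
| 10% | 50% | −ln(0.40) = 0.916 | × 10/60 = 0.153 | 14.2% | 4.2 |

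Other values of L behave similarly. With D = 16%, L = 5% gives 5.5% and L = 20% gives 22.0%. With D = 50%, they give 7.0% and 29.1%. The relative excess is about 9–10% at D = 16% and 40–46% at D = 50%.

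**Scale.** One patient in 20 is 5 points, so at L = 10% the whole bias is less than one patient's contribution.

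**Amputation exclusion.** The documents give no amputation rate. Assume 20 patients, two local recurrences among limb-salvage patients and two amputees:
- amputees excluded: 2/18 = 11.1%
- amputees kept, none recurring: 2/20 = 10.0%
- amputation counted as local failure: 4/20 = 20.0%

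Against the second figure the exclusion raises the estimate by about 1 point; against the third it lowers it by about 9. The direction depends on how amputation is regarded, which the documents do not settle.

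**The case against.** The strongest reply is that the plan does not contain this analysis. Section 11.2 covers the primary and secondary endpoints, and the local endpoint named among these is local disease-free survival. It counts death and has no amputation exclusion, so Kaplan-Meier is valid for it. No sentence says that deaths are censored in 9.5.1. This stands in part: censoring is an inference, and a reader should not take it as a stated rule. But 9.5.1 is a formal definition under the time-to-event heading, both endpoint lists are open, and the plan offers only one method. Whoever analyses 9.5.1 from this document has no other instruction.

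A second reply is that the effect is small. At the earlier regimen's 2-year mortality the excess is under 1 point. An exact 95% interval for 2 of 20 runs from about 1% to 32%, and the analysis is descriptive. This stands as to importance. It is not a reason to prefer an estimator with a known systematic error when the alternative costs almost nothing.

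A reader might also infer that excluding amputees discards the worst local outcomes and so understates local failure. The documents do not support that. If amputation is the primary operation, it is known at time zero, and the exclusion may simply define a limb-salvage population. Few amputations are to be expected given the entry criterion. Keeping amputees as non-recurrences lowers the estimate (2/20 against 2/18). What remains is that 9.5.1 does not say whether amputations after the primary operation also exclude a patient, which would condition on the future.

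**Conclusion.** The point holds as a minor one. With recurrence as the only event and Kaplan-Meier as the only method, following the plan as written implies censoring deaths, and one minus Kaplan-Meier would overstate cumulative local recurrence. At a true 10% the excess is about 1 point if 16% die first, 2 points if 30% do and 4 points if half do. These sizes rest on constant hazards and on assumed values of L and D.

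The upper figure should not be read as the expected bias. It takes a mortality statement without a time horizon, about high-grade deep tumours, and treats every such death as preceding local recurrence. The trial also admits grade 2 and superficial tumours, although admitting stage IV disease pulls the other way.

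Nothing in the primary analysis, the sample size or the listed survival endpoints is affected. The amputation exclusion is a matter of transparent reporting; its net direction cannot be found from the documents.

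**What to change.** In 11.2, add that time to local recurrence, if reported, is estimated by cumulative incidence (Aalen-Johansen) with death without local recurrence as a competing event, and that Kaplan-Meier is kept for the endpoints that include death.

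In 9.5.1, state whether the exclusion covers only amputation as the primary operation or later amputations as well. Report the number amputated, and give the estimate for all resected patients alongside the limb-salvage-only estimate.

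The cost is a few sentences, slightly more analysis work and one extra descriptive estimate. The methods are standard. Death and local recurrence are already followed under 8.6, so no new data are needed for the main change.
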